7.2.2 Screening/Baseline and Randomized Treatment (Day 1)

All required screening and baseline (pre-infusion Day 1) procedures/assessments will be performed prior to administration of the blinded study drug infusion.

Assessments include the following:

- Informed consent
- Inclusion/exclusion criteria
- Pregnancy test for females of child-bearing potential
- Record demography, (including age [year of birth], gender, race, and ethnicity) disease characteristics (date of exposure, date of onset)
- Ordinal Scale assessment
- National Early Warning Score (NEWS) ([Appendix 2](#))
- Record clinical features key symptoms: fever, cough, shortness of breath, fatigue, myalgia etc.
- Vital signs (temperature, systolic and diastolic blood pressure, pulse, respiratory rate)
- Weight
- Record result of historical SARS-CoV-2 PCR (qualitative RT-PCR) or NAT or other commercial or public health assay approved by regulatory authorities as a diagnostic test for COVID-19 in any specimen during the current hospital admission OR 96 hours prior to the hospital admission date and prior to randomization (the SARS-CoV-2 test results must be performed by a hospital laboratory and the documentation available) (eligibility criterion)
- If subject is receiving oxygen, record any supplemental oxygen administration (type, %, flow start/end date/time)
- Record hospital admission date
- Record oxygen saturation (specify on or off oxygen supplementation)
- Respiratory sample for quantitative measurement of SARS-CoV-2 viral load by NAT or PCR (real-time RT-PCR) (obtained via nasopharyngeal swab)

GRIFOLS Bioscience Industrial Group	Number	BIG-CL-PRT-000019	Version	6.0	Status	Effective	Effective Date	08-Dec-2021
	GC2006 -A Multicenter, Randomized, Open-label, Parallel Group Pilot Study to Evaluate the Safety and Efficacy of Prolastin®-CL Liquid plus Standard Medical Treatment (SMT) versus SMT alone in Hospitalized Subjects with						Page	52 of 94

- Sample for quantitative measurement of IgM and IgG antibodies to SARS-CoV-2 by enzyme linked immunosorbent assay (ELISA), Indirect Fluorescent Antibody (IFA), or another assay methodology (if antibodies cannot be determined at the site store *serum* samples frozen at -70°C for later analysis at an external lab)
- Serum Chemistry (creatinine, albumin, alanine aminotransferase [ALT], total bilirubin, lactate dehydrogenase [LDH])
- Calculate eGFR using the Cockcroft-Gault formula.

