The primary efficacy analysis will be carried out on the ITT population and repeated on the PP population (if different from the ITT population) by Fisher's exact test. Secondary and exploratory efficacy analyses will be analyzed by means of Kaplan-Meier survival estimates and curves and compared between treatment groups by means of the Log-rank test for time to event variables, analysis of covariance (ANCOVA) when adjusting for covariates, or analysis of variance (ANOVA) when without covariates for normally-distributed variables or Wilcoxon rank-sum test for non-normally-distributed variables. Detailed data handling and evaluation procedures and details of the interim review will be described in the Statistical Analysis Plan (SAP).

For the primary endpoint, if the value of the subject is missing, then a conservative imputation rule will be used such that the subject will be treated as having met the condition for the primary efficacy analysis. The choice of analysis method for primary, secondary and exploratory efficacy endpoints will be described in detail in the SAP which will be finalized and signed off before data analysis is performed.

The SAP may include exploratory analyses of various aspects of SMT inclusive of different interventional strategies and evolving treatment modalities. Grifols will analyze the use of COVID-19 specific, potentially disease modifying treatments for any potential differences between study arms. This analysis will be fully detailed in the SAP since medical understanding of COVID-19 interventions is rapidly evolving. For ethical reasons, there are no restrictions placed on what are perceived to be potentially life-saving therapies (apart from participation in another interventional clinical trial).

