## 3.2 Treatment

### 3.2.1 Randomization Scheme and Treatment Arm Assignment

Subjects will be randomized 1:1 to receive either combination treatment with Liquid Alpha1-PI (Human) plus SMT or placebo plus SMT.

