## 4. GENERAL CONSIDERATIONS FOR DATA ANALYSIS

Unless otherwise specified, continuous variables will be summarized using descriptive statistics

(n, mean, standard deviation, median, minimum, and maximum). Categorical variables will be summarized showing the number and percentage of subjects within each category.

Summary results will be provided for each treatment group. All tabulations will be based on pooled data across centers.

All statistical tests will be two-sided and tested at the 5% level of significance.

Analyses will be performed using SAS for Windows statistical software, version 9.4 or higher (SAS, Cary, NC), except where other software may be deemed more appropriate. In the event that other software is used to perform some analyses, the details will be provided in the Clinical Study Report.

██████████ will perform all efficacy and safety analyses described in this SAP and Grifols will review them.

Subject data will be listed, sorted by treatment group and subject number. When applicable, listings will be additionally sorted by visit and assessment date/time.

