### 6.1 Primary Efficacy Endpoint and Analysis

The primary efficacy analysis will be carried out on the ITT population. If there is difference between the PP population and ITT population, the analysis will be repeated using the PP population.

The primary efficacy variable is the proportion of subjects who die or require ICU admission on

or before Day 29, or who are dependent on high flow oxygen devices or invasive mechanical ventilation on Day 29. The primary efficacy endpoint will be derived based on the subject status (Alive/Death), ICU admission, mechanical ventilation and oxygen administration recorded in the database. Subjects who met any of the criteria listed below will be treated as meeting the primary efficacy endpoint:

- 1) Death is recorded on the eCRF All Visits page “General Duration of Hospitalization, & Overall Requirement for Mechanical Ventilation, ICU Admission and/or Oxygen Supplementation”;
- 2) ICU admission date is recorded on the eCRF All Visits page “General Duration of Hospitalization, & Overall Requirement for Mechanical Ventilation, ICU Admission and/or Oxygen Supplementation”;
- 3) On the eCRF Day 29 page “Mechanical Ventilation and Oxygen Administration”:
  - a. subject on mechanical ventilation is recorded in the mechanical ventilation record for that day, i.e., “Is the subject on a ventilator?” is recorded as “Yes”;
  - Or
  - b. the modality of oxygen administration is recorded as “High flow oxygen devices”

If for a subject any of the 4 criteria above could not be assessed due to missing data, then the subject will be treated as meeting the endpoint in the primary efficacy analysis.

The null hypothesis is that there is no difference in the proportions of subjects who met the primary endpoint between randomized groups;  $H_0: \pi_t - \pi_c = 0$ . The alternative hypothesis is that the proportions of subjects who met the primary endpoint are different between the treatment groups;  $H_1: \pi_t - \pi_c \neq 0$ .

The proportion of subjects who met the criteria for the primary endpoint within each treatment group will be presented along with a two-sided exact (Clopper-Pearson) 95% confidence interval (CI).

The observed difference in the proportion of subjects meeting the criteria between treatment groups along with the exact unconditional 95% CI for risk difference will be calculated. The null hypothesis will be tested using Chi-square statistic and the p-value will be reported.

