Subgroup analyses of the primary efficacy endpoint by baseline characteristics such as age group (with age cutoffs defined either by absolute values or by a summary metric [e.g., median] of the observed baseline values) and gender will be performed using the analysis method described above, if appropriate.

If for one or more subjects the actual treatment received is different from the randomized treatment and if deemed necessary, sensitivity analysis of the primary efficacy endpoint will be performed by repeating the primary efficacy analysis as described above in this section, but with subjects grouped according to the actual treatment received instead of the randomized treatment.

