## **6.2 Secondary Efficacy Endpoints and Analyses**

### **Assessment of clinical severity**

The NEWS will be calculated based on 7 clinical parameters and recorded on the eCRF. The

absolute value and change from baseline in the total score from Day 1 through Day 29 will be summarized by treatment group and visit using descriptive statistics.

Change in NEWS total score through Day 29 will be evaluated by fitting a linear mixed-effects model for repeated measures (MMRM). The model will include change from baseline in NEWS total score as the repeated dependent variable; treatment (as a class variable), visit (as a class variable), and treatment-by-visit interaction as fixed effects; baseline NEWS total score, age and gender as covariates; and measures within subject at each visit as a repeated measure. An unstructured covariance matrix will be used to model the within-subject error. If the fit of the unstructured covariance structure fails to converge, a compound symmetry covariance structure will be used. Parameters will be estimated using restricted maximum likelihood with the Kenward-Roger method for calculating the denominator degrees of freedom. Data collected starting at the Day 2 visit and up to the Day 29 visit will be included in this analysis. Missing data will not be imputed. From this model, the least-squares (LS) means and 95% CIs for each treatment group, the treatment difference in the LS means, the 95% CI for the difference, and the associated p-value will be reported on Days 15 and 29, as well as for the average across all post-baseline visits.

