## 9. SAMPLE SIZE AND POWER CALCULATIONS

Because of the urgency and lack of previous prospective COVID-19 data, sample size estimation remains incompletely defined; however, the size of this pilot study is commensurate with other Phase 2 investigations ongoing during the COVID-19 pandemic. Approximately 100 subjects are allowed to be randomized as part of a humanitarian effort against COVID-19.

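### The primary chi-square test is valid but leaves age and baseline severity unused, and no adjusted primary analysis is prespecified: a modest gain in precision is forgone

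*SAP*

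**What the plan says.** SAP 6.1 compares the proportions meeting the composite endpoint in the ITT population: "The null hypothesis will be tested using Chi-square statistic and the p-value will be reported". It adds Clopper-Pearson intervals per arm and an exact unconditional interval for the risk difference. None of these uses a covariate. Protocol 9.1 names a different but equally unadjusted test, with the analysis "repeated on the PP population (if different from the ITT population) by Fisher's exact test". Testing is at the usual level (SAP 4: "All statistical tests will be two-sided and tested at the 5% level of significance").

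Allocation is described only as "Subjects will be randomized 1:1 to receive either combination treatment with" the active product or placebo, each on top of standard treatment; no stratification factor is named. On size, SAP 9 says "Approximately 100 subjects are allowed to be randomized as part of a humanitarian effort against COVID-19", with no power, control rate or effect size.

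Protocol 7.2.2 lists age and "Ordinal Scale assessment" at Screening/Baseline and allows randomization only after those assessments are complete. Protocol 2 reports older age as a risk factor for death.

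Elsewhere the SAP does adjust. The NEWS model in 6.2 has "baseline NEWS total score, age and gender as covariates", the ordinal-scale model is similar, and the duration and proportional-odds models may adjust for age and gender. For the primary endpoint, age enters only through "Subgroup analyses of the primary efficacy endpoint by baseline characteristics such as age group" and gender, by the same unadjusted method. The one adjusted analysis that could reach the primary endpoint (SAP 5.6) is conditional, post hoc, and concerns concomitant COVID-19 medication.

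**The concern.** With about 100 subjects and no power basis, precision is scarce. Exclusion 1 removes invasive ventilation, ICU need and PaO2/FiO2 of 150 or less, which leaves baseline ordinal categories of roughly 3 to 5. A subject on high flow oxygen at entry is already in a state that counts as an event if it persists on Day 29, so baseline category is plausibly prognostic; the protocol itself says so of age. An analysis that ignores prognostic baseline values has a wider standard error than it needs. If the arms also differ by chance in baseline severity, the only adjusted estimate of the primary effect would be an unplanned one, chosen after the imbalance was seen.

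**Working it through.** **Inputs from the documents.** About 100 subjects, 1:1, so n = 50 per arm; two-sided alpha 0.05; unadjusted test. There is no planned power figure to reproduce. Event rates, treatment effect, category mix and covariate strength are all assumptions below.

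**1. Unadjusted power.** Power = Φ{(|Δ| − 1.96·√[2p̄(1−p̄)/n]) / √[(pc(1−pc) + pt(1−pt))/n]}. For 30% v 15%: Δ = 0.15 and p̄ = 0.225, so the null SE is √(2 × 0.225 × 0.775/50) = 0.0835 and the alternative SE is √((0.21 + 0.1275)/50) = 0.0822. Then (0.15 − 0.1637)/0.0822 = −0.167, and power is 43.4%.

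**2. Gain if the covariates explain a share R² of outcome variance.** Effective N = 100/(1 − R²).

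| Control v active | R² = 0 (N 100) | 5% (N 105) | 10% (N 111) | 20% (N 125) |
|---|---|---|---|---|
| 20% v 10% | 28.6% | 29.9% | 31.3% | 34.5% |
| 30% v 15% | 43.4% | 45.3% | 47.3% | 51.9% |
| 40% v 20% | 59.0% | 61.2% | 63.6% | 68.9% |

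**3. Simulation, chi-square v logistic score test** adjusted for category (3 v 4-5) and age. Assumed: 50 per arm, 4,000 trials per row, treatment odds ratio 0.35, age SD 14 years.

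| In category 3 | Risk, cat. 3 v rest | Age OR per 10 y | Chi-square power | Adjusted power |
|---|---|---|---|---|
| 15% | 45% v 20% | 1.0 | 46.1% | 46.1% |
| 20% | 50% v 18% | 1.5 | 42.7% | 45.8% |
| 25% | 55% v 15% | 1.5 | 39.3% | 45.1% |
| 25% | 55% v 12% | 2.0 | 33.4% | 41.3% |

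The gain runs from 0 to 7.9 points. Null rejection was 5.4% adjusted against 4.7 to 5.6% for the chi-square. With only 5% of subjects in category 3 and an age odds ratio of 1.2, power went from 44.6% to 43.9%, which is no gain. In another run (20% in category 3, age odds ratio 1.0) power rose from 43.2% to 44.6%, but size rose from 4.9% to 5.7%; at equal size the gain vanished.

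**4. Adjusted risk difference with a Wald test** (2,500 trials per scenario). Relative efficiency was about 0.98 with non-prognostic covariates and, with a treatment effect present, 1.02 to 1.05 for moderate and 1.08 to 1.18 for strong ones. Gains reached 10 points, but null rejection was 5.3 to 6.7% with prognostic covariates, so part of that is size. Relative efficiency is the cleaner measure here.

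**5. Chance imbalance.** If K of 100 subjects are in category 3 and k of them fall in one arm of 50, the arm difference is |2k − K|/50. It reaches 10 points when |2k − K| ≥ 5, with k hypergeometric (100, K, 50). For K = 15, 16, 18, 20, 22, 24, 25 the probabilities are 26.2, 17.1, 19.2, 21.1, 22.7, 24.1 and 35.6%. Even K needs a gap of 6, so its probabilities are lower; computing only K = 15 and K = 25 would miss this. The range is 17 to 36%.

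**The case against.** The chi-square is a valid test in a randomized trial, and its type I error already allows for chance imbalance. The SAP calls the study exploratory and a pilot. All of that stands: a reader might infer that the planned test is wrong or biased, and the documents do not support that.

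The gain may also be small. Excluding ICU need and low PaO2/FiO2 may leave few subjects in category 3. That category includes non-invasive ventilation, which is not named as a Day 29 component, so its prognostic strength is an inference. Counting unassessable outcomes as events weakens any covariate link further. This stands too, and it is why the range starts at zero.

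A reader might also take the missing adjustment as the cause of low power. It is not: risk-halving effects at control rates of 20 to 40% stay below 80% even with R² of 20%. The main cause is about 100 subjects with no power basis. Nor does the absence of a named stratification factor show that randomization was unstratified; the documents are simply silent.

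Finally, changing SAP 6.1 has side effects. SAP 8.2 applies the 6.1 methods at the futility look, where events are fewer still than the roughly 16 to 19 expected at the end in these scenarios. Protocol 9.1 still names Fisher's exact test. These points shape the fix but do not remove the forgone precision.

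**Conclusion.** The point holds as a prespecification improvement. The plan tests its primary endpoint validly but ignores two baseline measurements that it will hold for every subject, while adjusting a secondary endpoint for comparable ones. The gain at 50 per arm is about 0 to 8 power points: none if the covariates are weak, with about a 2% efficiency loss if they are not prognostic. Adjusted type I error is about 5 to 6% without a small-sample correction. Every one of these figures depends on assumed event rates, category mix and covariate strength, because the documents supply none. A 10-point imbalance in category 3 would arise in 17 to 36% of trials if 15 to 25 of 100 subjects start there. The direction is well supported; the size is not fixed by the documents.

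**What to change.** Before unblinding:

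- **SAP 6.1.** Prespecify an adjusted primary analysis with only two covariates, baseline ordinal category (3 versus 4-5) and continuous age. Use the score test for treatment from a logistic model, and report a standardised risk difference with a small-sample robust 95% CI. To hold size more strictly, take the p-value from a randomization-based test that follows the actual allocation scheme.
- **Fallback.** State in advance that if events are too sparse for the model to be fitted, the Cochran-Mantel-Haenszel test stratified by baseline category replaces it.
- **Sensitivity.** Keep the present chi-square p-value and the exact unconditional interval.
- **SAP 8.2.** State that the futility analysis of the primary endpoint and its conditional power stay on the unadjusted chi-square z-score, not the revised 6.1 method.
- **Protocol 9.1.** Align the named primary test with the SAP.

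The cost is SAP and protocol wording and a little programming; no new data are needed. The downsides are an estimate standardised through a model, slight size inflation if the small-sample correction is left out, and a conditional power that predicts a chi-square result and no longer the primary test.

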#### 4.5 Multiple Comparisons

Because of the exploratory nature of this study, there will be no adjustment for multiple comparisons.

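### SAP 6.1 plans separate chi-square p-values within age and gender subgroups but no treatment-by-subgroup interaction test, so those p-values do not show whether the effect differs between subgroups

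*SAP*

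**What the plan says.** SAP 6.1 first sets out the primary analysis: the proportion in each arm with a Clopper-Pearson interval, the risk difference with an exact unconditional 95% CI, and then a test: "The null hypothesis will be tested using Chi-square statistic and the p-value will be reported". SAP section 4 fixes the level: "All statistical tests will be two-sided and tested at the 5% level of significance".

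Later in 6.1, subgroup analyses by baseline characteristics such as age group "and gender will be performed using the analysis method described above, if appropriate". The age grouping is left open, "with age cutoffs defined either by absolute values or by a summary metric" such as the median of the observed baseline values. On multiplicity, SAP 4.5 says that "there will be no adjustment for multiple comparisons", and gives the exploratory nature of the study as the reason.

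The only interaction named in the SAP is treatment-by-visit, in the repeated-measures model for NEWS in 6.2 (the ordinal-scale model is described as similar). Neither document contains a treatment-by-subgroup term or a heterogeneity test, and neither says how subgroup results will be interpreted.

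**The concern.** A subgroup analysis is normally read as asking whether the treatment effect differs between groups. A p-value inside each group answers another question: whether the effect in that group differs from zero. When the two groups give p-values on opposite sides of 0.05, the natural reading is that the drug works in one and not in the other. With about 25 subjects per arm in each half, that pattern arises easily by chance when the effect is the same in both. The plan offers no statistic that would correct the reading.

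What is at stake is the interpretation of the subgroup tables in the study report.

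**Working it through.** **Inputs from the documents.** Two-sided alpha 0.05 (SAP 4). About 100 subjects: "Approximately 100 subjects are allowed to be randomized as part of a humanitarian effort against COVID-19" (SAP 9). Equal allocation: "Subjects will be randomized 1:1 to receive either combination treatment" (SAP 3.2.1). This gives about 50 per arm, and a median age split gives about 25 per arm in each half. The chi-square test is taken without continuity correction, in line with the z-score in SAP 8.2.

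**Inputs assumed.** The documents state no event rate, effect size, power or gender split, so there is no planned figure to reproduce. I used a range of control and treated rates, the same rates in both subgroups, and splits of 25/25, 30/20 and 35/15 per arm.

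**Step 1: power within a subgroup.** Exact binomial enumeration of the chi-square test gives the rejection probability in each subgroup, A and B.

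**Step 2: significant in exactly one of two.** The subgroups share no subjects, so P(exactly one) = A(1 − B) + B(1 − A). With an even split, A = B and this is 2A(1 − A).

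| Control v treated | Full-trial power | A (25 per arm) | P(exactly one) |
|---|---|---|---|
| No effect (nominal) | 5% | 0.050 | 2 × 0.050 × 0.950 = 9.5% |
| 10% v 5% | 15% | 0.081 | 2 × 0.081 × 0.919 = 15% |
| 15% v 10% | 12% | 0.086 | 2 × 0.086 × 0.914 = 16% |
| 30% v 20% | 21% | 0.135 | 2 × 0.135 × 0.865 = 23% |
| 20% v 10% | 30% | 0.174 | 2 × 0.174 × 0.826 = 29% |
| 30% v 15% | 44% | 0.257 | 2 × 0.257 × 0.743 = 38% |
| 40% v 20% | 60% | 0.352 | 2 × 0.352 × 0.648 = 46% |
| 35% v 15% | 65% | 0.389 | 2 × 0.389 × 0.611 = 47.5% (47% by simulation) |
| 30% v 10% | 73% | 0.450 | 2 × 0.450 × 0.550 = 50% |
| 40% v 15% | 82% | 0.532 | 2 × 0.532 × 0.468 = 50% |

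With no effect, exact values are 9% to 11%. For moderate to large effects, uneven splits widen the range to 22% (30% v 20%, split 30/20) and 56% (30% v 8%, split 35/15). The even-split value peaks at 50% when A = 0.5, which corresponds to about 80% power for the whole trial.

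If the overall test is significant, exactly one subgroup is significant in 57% to 66% of trials (normal approximation, full-trial power 80% down to 30%).

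**Step 3: the interaction test on the same data.** Let d1 and d2 be the two subgroup risk differences. The contrast is d1 − d2, with variance equal to the sum of p(1 − p)/n over the four cells. Under a uniform effect it rejects 5% of the time by normal approximation, and about 6% by simulation of the Wald test with 25 per cell. Of the trials significant in one subgroup only, about 10% to 15% would also have a significant interaction (full-trial power 80% down to 30%).

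**Step 4: what the interaction test can detect.** Suppose 35% v 15% in one age half and 35% v 35% in the other. Variance = (3 × 0.35 × 0.65 + 0.15 × 0.85)/25 = 0.810/25 = 0.0324, so SE = 0.18. The true contrast is 0.20, and 0.20/0.18 = 1.11. Power is about 20% by normal approximation and 22% by simulation. The same simulation gives 15% for 30% v 15% in one half only, and 40% for 40% v 10% in one half only.

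**The case against.** The case for leaving the text alone has real substance.

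- **No decision rests on subgroups.** A reader might infer that the SAP judges subgroup effects by whether p falls below 0.05. The text sets no such rule and makes no claim of heterogeneity. Nor do the documents say that subgroup results will decide who is studied next.
- **Estimates are already planned.** The method carried into the subgroups includes risk differences with exact 95% CIs, so it would be wrong to say that only p-values are reported.
- **The study is openly exploratory.** Subgroup analyses run only where appropriate, and SAP 8.2 excludes them from the futility analysis. With no effect, at least one of four age and gender p-values falls below 0.05 in about 16% to 17% of simulated trials. That is ordinary multiplicity, which SAP 4.5 accepts.
- **The size depends on assumed rates.** The 47% at 35% v 15% reflects a large effect.
- **The age wording offers alternatives.** A reader might infer that several splits will be tried. The text more naturally offers two ways to define one split, and a pooled baseline median does not depend on outcome or treatment.
- **The interaction test is weak here,** as step 4 shows.

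All of this limits the point. What remains is that the SAP asks for within-subgroup p-values that do not answer the subgroup question, plans nothing that does, and does not say when the age split is fixed. Being exploratory explains the lack of multiplicity adjustment, but it does not make the p-values informative about heterogeneity.

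**Conclusion.** The point holds as a gap in the subgroup analysis. The planned p-values cannot show whether the effect differs by age or gender. A uniform effect would appear significant in exactly one of two subgroups in roughly 22% to 56% of trials per factor for moderate to large effects, and in about 10% to 16% for nil or very small ones, against about 5% to 6% false declarations from an interaction test.

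These figures rest on assumed event rates, on about 50 per arm, and on equal risks in the two subgroups. The last is a simplification for age, since protocol section 2 cites older age as a risk factor for death. The figures show how large the problem could be and do not predict this trial. The documents do not support a stronger conclusion that the primary result or its type I error, or the futility decision, is affected.

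**What to change.** In SAP 6.1:

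1. Keep the subgroup proportions and risk differences with 95% CIs as planned.
2. Drop the within-subgroup chi-square p-values, or label them descriptive.
3. For each factor, add one treatment-by-subgroup interaction estimate with 95% CI and p-value. State its scale; the difference between subgroup risk differences matches the primary analysis.
4. Name a single age split before unblinding, either a fixed value or the pooled baseline median.
5. State that a non-significant interaction is not evidence of a uniform effect.

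The cost is a few lines of SAP text and one contrast per factor, with no new data. The downsides are fewer p-values and low power at about 100 subjects: about 22% to detect 35% v 15% in one age half and no effect in the other. The interval for the interaction will usually be wide, and should be read as such.
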